At the time of screening, patients must have a MMSE score of ≥ 20 points and a Clinical Dementia Rating–Global Score (CDR-GS) of 0.5 or 1.0. To confirm objective memory impairment, patients must also have a Repeatable Battery for the Assessment of Neuropsychological Status (RBANS) Delayed Recall Index of ≤ 85 at the time of screening. Patients will be eligible for the study whether or not they are receiving standard-of-care symptomatic medications for AD (e.g., cholinesterase inhibitors, memantine, and/or the medical food supplement Souvenaid®). These medications must have been stable for ≥ 2 months prior to screening, and there should be no a priori planned initiation, discontinuation, or dose changes for these medications during the study (including during the double-blind treatment and OLE treatment periods). However, following the initiation of study drug, standard-of-care symptomatic medications for AD may be initiated, dose adjusted, or discontinued as deemed clinically appropriate.

See Section 4.1 for further details of the inclusion and exclusion criteria.

To monitor patients for safety, the incidence and nature of adverse events, serious adverse events, adverse events of special interest, responses on the Columbia-Suicide Severity Rating Scale (C-SSRS), and abnormalities in standard safety blood *and urine* tests, ECG, *vital signs, physical examination*, and MRI will be assessed on a regular basis by the Sponsor and an unblinded iDMC. Blood samples will be obtained from all patients for the assessment of pharmacokinetics and for the measurement of antibodies directed against MTAU9937A and other components of the drug product.

Baseline measures of COAs (for clinical efficacy) and tau biomarkers (for PD activity) will be obtained prior to the initiation of study drug, either during the screening period

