4.2 METHOD OF TREATMENT ASSIGNMENT AND BLINDING

Patients will be randomly assigned to one of three active, IV dose arms (1500, 4500, or 8100 mg MTAU9937A) or to an IV placebo dose arm in a 2:3:2:3 (1500mg:4500 mg: 8100 mg:placebo) ratio. Randomization of patients will be managed by a central interactive voice or Web-based response system (IxRS) vendor using stratified permuted block randomization. The randomization will be stratified by dementia status (pAD vs. mAD) and APOE status (ApoE4+ vs. ApoE4-).

Patients, study site personnel who will evaluate patient status, contract research organization (CRO) personnel who will review CRFs, other Sponsor agents (with the exception of the IxRS vendor), and the Sponsor will remain blinded to treatment assignment. The unblinded site pharmacist and the unblinded CRO monitor will be unblinded to treatment assignment.

The iDMC and independent data coordinating center vendor will be unblinded to treatment assignment.

Although PK samples must be collected from participants assigned to placebo to maintain the blinding of treatment assignment, PK assay results for the placebo participants are generally not needed for the safe conduct or proper interpretation of this trial. Laboratory personnel responsible for performing PK assays will be unblinded to participants' treatment assignments to identify appropriate PK samples to be analyzed. Samples from participants assigned to the placebo arm will not be analyzed except by request (e.g., to evaluate a possible error in dosing).

If unblinding is necessary for immediate patient management (e.g., in the case of a serious adverse event for which patient management might be affected by knowledge of treatment assignment), the investigator will be able to break the treatment code by contacting the IxRS. The investigator is not required to contact the Medical Monitor prior to breaking the treatment code; however, the treatment code should not be broken except in emergency situations. If the investigator wishes to know the identity of the study drug for any reason other than a medical emergency, he or she should contact the Medical Monitor directly. The investigator should document and provide an explanation for any non-emergency unblinding. The investigator will be able to break the treatment code by contacting the IxRS.

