4.4 CONCOMITANT THERAPY

Concomitant therapy consists of any medication (e.g., prescription drugs, over-the-counter drugs, vaccines, herbal or homeopathic remedies, nutritional supplements) used by a patient in addition to protocol-mandated treatment from *3 months* prior to *the start of* screening until the final study visit. However, any agent that targets A β used by the patient at any time during their life is also considered to be a concomitant therapy. All such medications should be reported to the investigator and recorded on the appropriate Concomitant Medications eCRF.

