4.5.2 Medical History, Concomitant Medication, and Demographic Data

Medical history, including clinically significant diseases, surgeries, cancer history (including prior cancer therapies and procedures); reproductive status; smoking history; and use of alcohol and drugs of abuse; and recent history (5 years) of non-elective hospitalizations, pneumonia or cardiovascular events, will be recorded at baseline.

In addition, all medications (e.g., prescription drugs, over-the-counter drugs, vaccines, herbal or homeopathic remedies, nutritional supplements) used by the patient within *3 months* prior to initiation of screening until the final study visit will be recorded. Any agent that targets A β used by the patient at any time during their life (any time before initiation of screening and while on study) will also be recorded. At the time of each follow-up physical examination, an interval medical history should be obtained and any changes in medications and allergies should be recorded.

Demographic data will include age, sex, self-reported race/ethnicity, and years of education. Demographic data will be collected for both the patient and the caregiver.

As this study is being conducted in multiple geographic regions, it is likely that patients of different ethnic origins will be enrolled in the study. Although there is currently no indication that MTAU9937A is metabolized or eliminated differently or that the treatment effect would be different in patients with different ethnic origins, collecting this information (where permitted by local regulations) is essential to adequately evaluate the results of this study (e.g., possible differences in PK exposure [concentration of the drug in the blood] or treatment effect).

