3. STUDY CONDUCT

3.1 RANDOMIZATION ISSUES

Patients will be randomly assigned to one of three active, IV dose arms (1500, 4500, or 8100 mg MTAU9937A) or to an IV placebo dose arm in a 2:3:2:3 (1500mg:4500 mg: 8100 mg:placebo) ratio. Randomization of patients will be managed by a central interactive voice or Web-based response system (IxRS) vendor using stratified permuted block randomization. The randomization will be stratified by dementia status (pAD vs. mAD) and APOE status (ApoE4+ vs. ApoE4-). The iDCC vendor periodically checks the IxRS to ensure that randomization is being performed correctly and that the correct kits are being assigned.

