4.4 EFFICACY ANALYSIS

All efficacy analyses will be based on the modified intent-to-treat populations defined in Section 4.1.2. The primary and secondary endpoints will be analyzed as change scores, calculated as follows:

Outcome measure change score = (post-baseline value – baseline value)

In the above determination of change score for CDR-SB and RBANS, the baseline value will be defined as the average of all non-missing values before the first dose of study drug, which should be an average of the screening and baseline values. For all other cognitive and biomarker endpoints, baseline value will be defined as latest observed value before the first dose of study drug.

For the primary and secondary endpoints, mean changes from baseline will be compared across treatment arms using mixed-models for repeated measures (MMRM). Each model will have an intercept term, a term for baseline value of the endpoint, a term for APOE4 strata (carrier vs. non-carrier), a term for dementia status strata (pAD vs. mAD), an interaction term of the two stratification factors, categorical visit terms, a term for treatment group, a term for baseline age, and terms for treatment-by-visit interactions. This will be implemented using SAS proc mixed syntax similar to the excerpt below:

```
proc mixed data=data;  
class PATNUM VISIT TRT APOE4 DEMSTATUS;  
model var = BASE BAGE APOE4 DEMSTATUS APOE4*DEMSTATUS VISIT TRT TRT*VISIT  
/solution noint ddfm=kr;  
repeated VISIT / subject=PATNUM type=UN;  
lsmeans VISIT*TRT / pdiff cl alpha=0.05;  
estimate 'MTAU9937A vs Placebo Wk 73' TRT -1 1/cl;
```

An unstructured variance-covariance matrix for within-subject errors will be assumed. If the unstructured covariance structure matrix results in a lack of convergence, the heterogeneous Toeplitz covariance structure followed by the heterogeneous first-order autoregressive

covariance structure will be used. In these cases, the sandwich estimator will be used to get the variance of the treatment effect estimator.

If model assumptions are violated (e.g. large deviations from normality of residuals), alternative modeling strategies including data transformations, permutation-based approaches, and/or robust mixed effects modeling methodology (Koller, Journal of Statistical Software 2016) will be used as appropriate for additional sensitivity analyses.

Comparisons of Interest

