4.4.3 Sensitivity Analyses

Mixed-models for repeated measures (MMRM) methods have been selected for the primary and secondary analyses due to their ability to accommodate the potential effects of missing data. An advantage of such models is that they rely on the assumption that the missing data mechanism is missing-at-random (MAR), rather than the more restrictive assumption that it is missing-completely-at-random (MCAR).

To evaluate the robustness of MMRM analyses to potential effects of missing data and validity of the MAR assumption, sensitivity analyses will be performed in the mITT population for the co-primary and secondary endpoints. At each time point (Week 25, Week 49, and Week 73), an ordinary least squares model for the change scores at that timepoint will be fit to estimate the treatment effect. These models will have terms for the baseline value of the endpoint, APOE4 strata, dementia status strata, the interaction between APOE4 strata and dementia status strata, baseline age, and treatment effect. These models will be fit using the following imputations for missing data:

- No imputation (a completer analysis)
- Using linear extrapolation imputation based on the values at baseline and the last week with a non-missing value
- Using last-observation-carried-forward
- Tipping point analysis

Intercurrent events may also influence the primary endpoint even if they do not directly result in missing data. Additional sensitivity analyses will be conducted using the above methods, but treating data collected after a given intercurrent event as missing. Proposed intercurrent events include missed study drug administration and initiation or modification of AD symptomatic concomitant medications. A separate section detailing intercurrent events and protocol deviations due to COVID-19 is included below. We propose to apply the same set of sensitivity analyses listed above when considering this additional set of intercurrent events.

Additional analyses looking at treatment effect estimates in subpopulations of patients receiving at least a minimum number of doses will also be conducted to assess if any observed treatment effect could have been potentially diluted by patients who did not fully adhere to the study drug administration schedule.

COVID-19 Sensitivity Analyses

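### Baseline symptomatic AD medication is recorded but enters no efficacy model; adding it before unblinding is a small, nearly free gain in precision, not the repair of an error

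*SAP*

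**What the plan says.** Entry is open to both groups: "Patients will be eligible for the study whether or not they are receiving standard-of-care symptomatic medications for AD" (Protocol 3.1.1). Protocol 4.1.1 and 4.4.1 require a regimen that has been stable for 2 months before screening.

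Use is captured from 3 months before screening: "All such medications should be reported to the investigator and recorded on the appropriate Concomitant Medications eCRF" (Protocol 4.4), with the same look-back in Protocol 4.5.2.

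Allocation does not balance it: "The randomization will be stratified by dementia status (pAD vs. mAD) and APOE status" (Protocol 4.2; SAP 3.1 repeats this).

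The text of SAP 4.4 ends its list of terms for the primary model with "a term for treatment group, a term for baseline age, and terms for treatment-by-visit interactions", and the code there is "model var = BASE BAGE APOE4 DEMSTATUS APOE4*DEMSTATUS VISIT TRT TRT*VISIT". The model goes beyond the strata, since it adds baseline score, the strata interaction and age, but it has no medication term. Protocol 6.4.1 adjusts only for ApoE4 and clinical status. The ordinary least squares models of SAP 4.4.3 use the same baseline covariates as the MMRM. The subgroup list in SAP 4.4.4 omits medication, and the open-ended baseline table in SAP 4.3 does not name it.

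The SAP's efficacy analyses take up these drugs only as a post-baseline event: "Proposed intercurrent events include missed study drug administration and initiation or modification of AD symptomatic concomitant medications" (SAP 4.4.3).

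**The concern.** Background symptomatic treatment is fixed before the first dose, is already in the database, and could plausibly relate to the outcome. If it does, an imbalance between arms that arises by chance moves the estimated difference by the imbalance times the prognostic difference, and no planned analysis would remove or display that movement.

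The first hypothesis test has a stated power of only 68%, and every later formal test waits on it (SAP 4.4, Type I Error Management). A small gain in precision there is worth having if it costs almost nothing. The model already contains one non-stratum baseline characteristic (age), so it is not restricted to the stratification factors.

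**Working it through.** **Inputs from SAP 2.2:** 228 pooled active and 137 placebo patients before dropout; 25% dropout; SD 2; true difference 0.6; alpha 0.05, two-sided (SAP 4.4).

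**Reproducing the plan's figures.** Completers: 228 × 0.75 = 171 and 137 × 0.75 = 102.75.
- SE = 2 × sqrt(1/171 + 1/102.75) = 0.250.
- Power = Φ(0.6/0.2496 − 1.96) = Φ(0.443) = 67.1% (66.8% with the noncentral t), against 68% stated.
- The 90% interval for 4500 mg versus placebo is 0.6 ± 1.645 × 2 × sqrt(2/102.75) = 0.14 to 1.06, as stated.

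**Assumptions, because the documents give no figures:** share of users p = 0.3 to 0.7; difference between users and non-users in Week 73 CDR-SB change, after the existing covariates, g = 0.25 to 1.0 points. The planning SD of 2 is used as the residual SD.

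**Chance imbalance in the first test.** SD = sqrt(p(1−p)(1/171 + 1/102.75)), which is 5.7 percentage points at p = 0.3 or 0.7 and 6.2 at p = 0.5. The 95% range is ±11 to ±12 points.

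**Shift in the contrast and effect of adjusting.** Shift = imbalance × g. Variance explained: R² = p(1−p)g²/4. Adjusted SE = 0.2496 × sqrt(1 − R²).

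| g | 95% range of shift | R² | Adjusted SE | Power with the term |
|---|---|---|---|---|
| 0.25 | ±0.03 | 0.003-0.004 | 0.249 | 67.3% |
| 0.5 | ±0.06 | 0.013-0.016 | 0.248 | 67.7-67.8% |
| 0.75 | ±0.08 to ±0.09 | 0.030-0.035 | 0.245-0.246 | 68.4-68.7% |
| 1.0 | ±0.11 to ±0.12 | 0.053-0.063 | 0.242-0.243 | 69.5-69.9% |

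For 4500 mg alone versus placebo (102.75 per arm) the shift range runs from ±0.03 to ±0.14.

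For a given g and SD the power gains are upper bounds. The formula treats all variation in use as new information, whereas baseline CDR-SB, dementia status and age probably predict part of it.

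**Type I error.** A simulation of a single-visit comparison (171 versus 103 patients, p = 0.5, g = 1, 20,000 runs, Monte Carlo SE about 0.15 points) rejected a true null in 5.3% of runs without the term and 5.2% with it. Power was 67.2% and 69.7%. Conditional on a realised imbalance the picture differs slightly. At 10 points with g = 0.5, the shift is 0.05 (0.2 SE; 8% of 0.6) and the conditional error is 5.5%. With g = 1.0, the shift is 0.10 and the conditional error 6.9%.

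**Form of the term.** A single main effect imposes the same difference at Weeks 25, 49 and 73. Suppose instead that the difference grows linearly to Week 73, with visit SDs anywhere from 1.0/1.5/2.0 to equal at 2.0 and between-visit correlations of 0.4-0.7 (all assumptions). The generalised least squares constant then recovers only about 23-67% of the Week 73 difference. A medication-by-visit interaction avoids this loss.

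**The case against.** The strongest reply is that this is a preference among covariates. Randomisation makes the contrast unbiased, the MMRM standard error already allows for chance imbalance in unmodelled factors, and the same could be said of sex, education or region. That stands, and it is why the point is one of precision only. A reader might infer that the primary test is invalid, that its type I error is inflated, or that the 68% is wrong. The calculations support none of these.

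Second, nothing in the documents shows that baseline use is prognostic. A reader might infer that users progress faster or drop out differently, so that the term would also make the missing-at-random assumption safer. The documents give no decline or dropout by medication use, so both remain assumptions. Nor does SAP 4.4.3 concede the matter: starting or changing a drug after baseline can move a score away from baseline, which does not imply that stable use predicts change.

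Third, a stable symptomatic effect is already in the baseline score, which is both subtracted and adjusted for. This is only partly an answer. Protocol 1.1 describes the benefit of approved drugs as temporary and limited to some patients, so it need not cancel over 73 weeks.

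Fourth, these drugs are not the only permitted treatment that might act on cognition. Protocol 3.1.1 lists Souvenaid among the symptomatic medications, and Protocol 4.1.2 allows stable stimulants. The flag therefore needs an explicit definition.

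**Conclusion.** The omission is real and adjusting for it would be a minor improvement; it is not an error in the plan. Under the assumed ranges, leaving the term out exposes the first contrast to a chance shift whose 95% limits are about ±0.03 to ±0.12 points, at most about half of one standard error (0.12/0.25). Including it adds between roughly 0.2 and 2.8 percentage points of power (67.1% to 67.3-69.9%), as an upper bound. If use is not prognostic, essentially nothing is gained and almost nothing is lost. The size rests wholly on the assumed share of users and their assumed prognostic difference.

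**What to change.** Before unblinding:

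- Add to the SAP 4.4 MMRM, for CDR-SB and all four secondary endpoints, a binary term for symptomatic AD medication at first dose and its interaction with VISIT, in the text and in the CLASS and MODEL lines of the SAS code. None of the current baseline covariates interacts with visit, so state the reason: the adjustment should apply at Week 73.
- Define the flag: cholinesterase inhibitor and/or memantine, yes or no, saying whether Souvenaid counts.
- Include the main effect in the per-visit least squares models of SAP 4.4.3.
- Name the variable in the baseline table of SAP 4.3, so that any imbalance is visible.

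If the sponsor prefers to leave the primary model as it is, a named sensitivity model with the same terms is the minimum.

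The cost is one variable derived from existing concomitant-medication data, about one degree of freedom per visit, and some SAP wording. Enrolment is complete, so the strata cannot change, and nothing in trial conduct needs amending. Added after unblinding, the same adjustment would be post hoc.

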3.3.2 Rationale for Patient Population

The patient selection approach is consistent with the NIA-AA research diagnostic criteria and guidelines for AD as well as with the Qualification Opinion from the European Medicines Agency's Committee for Medicinal Products for Human Use on the use of CSF biomarkers and/or PET-amyloid imaging for enrichment of trials in mild to moderate AD dementia (2012), and U.S. Food and Drug Administration (FDA) draft guidance for early AD (2013). Although the FDA guidance refers to the early stage of AD in which individuals present with MCI, biomarkers of amyloid pathology are expected to add value to patient selection in mAD studies (see Section 3.3.3).

Patients in this study are also required to meet standard research criteria for mAD (according to the NIA-AA research criteria and guidelines for AD; [Appendix 3](#)) or pAD (according to the NIA-AA research criteria and guidelines for MCI; [Appendix 4](#)). Patients with pAD will present with documented objective evidence of deficit in at least one cognitive domain. Patients with mAD will present with documented deficits in at least two cognitive domains and in functional decline. Overall, the population will have an MMSE of ≥ 20 points and a CDR-GS of between 0.5 and 1.0. The MMSE score provides evidence of mild disease severity, and the CDR-GS score indicates that the patients have noticeable amnesic (pAD) or cognitive and functional deficits (mAD).

To ensure that the patients selected are likely to decline over the length of the study, two approaches have been included. The first is that all patients have to demonstrate amnesic deficits as measured by the Delayed Recall index of the RBANS (see Section 4.5.7.3). The Delayed Recall index of ≤ 85 has been selected, corresponding to one standard deviation below population-based normative data.

The second approach to ensure decline is to verify that there is evidence of prior decline through observations made by clinician or caregiver and recorded on the DVF. Enrollment into this study is subject to adjudication of diagnosis by the Sponsor or

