4.1.1 Inclusion Criteria

Patients must meet the following criteria for study entry:

- Signed Informed Consent Form by the patient (co-signed by the patient's legally authorized representative, if required by the local regulations, guidelines, and independent ethics committee [EC] or Institutional Review Board [IRB])
 - Patients should be judged by the investigator to be lucid and oriented when giving the informed consent.
- Age between 50 and 80 years, inclusive, at time of signing Informed Consent Form

- NIA-AA core clinical criteria for probable AD dementia (see [Appendix 3](#); McKhann et al. 2011) or pAD (consistent with the NIA-AA diagnostic criteria and guidelines for MCI; [Appendix 4](#); Albert et al. 2011)
- Evidence of the AD pathological process, by a positive amyloid assessment either on CSF A β ₁₋₄₂ as measured on Elecsys β -Amyloid(1-42) Test System OR amyloid PET scan by visual read by the core/central PET vendor as specified in the Imaging Review Charter

If a patient is amyloid negative based on CSF assessment, they may undergo an amyloid PET scan during screening to potentially be enrolled. The patient may undergo an LP for CSF assessment or an amyloid PET scan only one time each during screening.

If a patient is amyloid negative based on an amyloid PET scan, they may undergo an LP for CSF assessment during screening to potentially be enrolled. The patient may undergo an LP for CSF assessment or an amyloid PET scan only one time each during screening.

Under certain circumstances, a previously acquired amyloid PET scan may be used for study inclusion (see Section [4.5.8](#)). If the previously acquired amyloid PET scan is considered valid and is read negative by the core/central PET vendor, the patient may undergo CSF assessment to potentially enrollment, but the patient may not undergo an additional amyloid PET scan for enrollment.

- mAD symptomatology, as defined by a screening MMSE score of ≥ 20 points and CDR-GS of 0.5 or 1
- Abnormal memory function at screening as demonstrated by an RBANS Delayed Recall Index ≤ 85

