4.5.7.1 Mini-Mental State Examination

The MMSE is a brief clinical cognitive examination commonly used to screen for dementia and other cognitive deficits (Folstein et al. 1975), which has a total score of 0–30. The MMSE will be administered to patients at screening to determine eligibility for the trial and at other timepoints postbaseline.

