4.3 ANALYSIS OF TREATMENT GROUP COMPARABILITY

Demographic and baseline characteristics such as age, sex, race, ApoE4 status, and baseline MMSE score will be summarized with means, standard deviations, medians, and ranges for continuous variables and with frequencies and proportions for categorical variables, as appropriate. Summaries will be presented by treatment arm and overall.

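### The CDR-SB model leaves out baseline MMSE, which every eligible patient has before dosing, and may forgo some precision in the first test of the sequence

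*SAP*

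**What the plan says.** SAP 4.4 gives the primary model in prose and in SAS code, and the two agree on covariates: "model var = BASE BAGE APOE4 DEMSTATUS APOE4*DEMSTATUS VISIT TRT TRT*VISIT". Disease severity enters in two ways. One is baseline CDR-SB, for which "the baseline value will be defined as the average of all non-missing values before the first dose of study drug", so normally the mean of a screening and a baseline rating. The other is "a term for dementia status strata (pAD vs. mAD), an interaction term of the two stratification factors". No MMSE term appears.

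MMSE is nonetheless collected on everyone before dosing. Protocol 4.5.7.1 states that "The MMSE will be administered to patients at screening to determine eligibility for the trial", and the inclusion criteria (Protocol 4.1.1) require a "screening MMSE score of ≥ 20 points and CDR-GS of 0.5 or 1". The schedule in Protocol Appendix 1 marks MMSE again at the baseline visit. Protocol 3.3.2 treats it as a severity measure: "The MMSE score provides evidence of mild disease severity".

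The SAP's only stated use of the baseline score is descriptive (SAP 4.3): "Demographic and baseline characteristics such as age, sex, race, ApoE4 status, and baseline MMSE score will be summarized".

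**The concern.** A pre-dose covariate that predicts the outcome reduces the residual variance of the treatment contrast. If it is fixed before unblinding, it does so without biasing the comparison or affecting type I error. MMSE is a plausible candidate. It is a direct cognitive test, whereas CDR is an interview with patient and caregiver, and dementia status has only two levels. The SAP already goes beyond the stratification factors by including age and the baseline endpoint value, and gives no reason for stopping short of MMSE.

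The comparison affected matters. The pooled 4500 mg and 8100 mg test on CDR-SB comes first in the fixed sequence of SAP 4.4. If it fails, no later hypothesis is formally tested. With stated power of 68%, even a modest, nearly costless gain deserves consideration.

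**Working it through.** **Inputs.** From SAP 2.2: true difference 0.6 points; SD 2; dropout 25%; 228 pooled active and 137 placebo patients before dropout. From SAP 4.4: two-sided alpha 0.05. Not in the documents, so assumed over a range starting at zero: the partial R-squared of baseline MMSE for Week 73 CDR-SB change, given the planned covariates.

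**Step 1: reproduce the SAP's figure.** Completers: 228 × 0.75 = 171 and 137 × 0.75 = 102.75, about 274 in all.

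SE = 2 × √(1/171 + 1/102.75) = 0.2496.

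Power = Φ(0.6/0.2496 − 1.96) = Φ(0.444) = 67.1%. A noncentral t calculation gives 66.8%. Both agree with the stated 68% to within about a point.

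The SAP's 90% interval for 4500 mg against placebo follows from the same arithmetic: SE = 2 × √(2/102.75) = 0.279, and 0.6 ± 1.645 × 0.279 = 0.14 to 1.06. The SAP's planning figures are therefore consistent with a two-sample comparison of completers that credits nothing for covariates or repeated measures.

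**Step 2: add MMSE.** Multiply the SE by √(1 − R²), where R² is the partial R-squared. The equivalent size of this comparison is 365/(1 − R²), since 228 + 137 = 365.

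| Partial R² (assumed) | SE | Power | Equivalent patients |
|---|---|---|---|
| 0% | 0.250 | 67.1% | 365 |
| 2% | 0.247 | 68.0% | 372 |
| 5% | 0.243 | 69.4% | 384 |
| 10% | 0.237 | 71.7% | 406 |

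**Step 3: what would be needed.** Solving 0.6/(0.2496 × √(1 − R²)) = 1.96 + z for the target power gives R² = 6.4% for 70% (z = 0.524) and R² = 26.4% for 80% (z = 0.842).

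**Step 4: does a single MMSE slope deliver this?** The formula in Step 2 assumes the slope is fitted at Week 73. A main effect alone fits one slope across Weeks 25, 49 and 73. As an illustration on assumed values, let the true slope at those visits be one third, two thirds and all of its Week 73 size, let the SD rise to 2, and let the adjacent-visit correlation be 0.5 to 0.7. A Week 73 partial R-squared of 10% then acts like about 6% to 8%, and power is about 70% to 71% instead of 72%. An MMSE-by-visit term removes this shortfall.

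**The case against.** The strongest reply is that SAP 4.4 pre-specifies a reasonable adjustment set, that nothing in either document promises MMSE adjustment, and that the benefit is unproven. Most of this stands.

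- **Incremental value is not shown.** Only what MMSE adds beyond a two-assessment mean CDR-SB, dementia status, age and APOE4 counts. Entry restricts MMSE to 20–30, and CDR itself rates memory, orientation and problem solving. The gain could be nil, so the range has to start at zero.
- **The starting SE may not be the planned model's.** The documents do not say whether SD 2 is raw or covariate-adjusted. If it is raw, the planned model may already do better than 68%.
- **MMSE is not the only candidate.** RBANS and ADAS-Cog 13 are also measured before dosing, and the documents do not rank them. MMSE has the practical merit of being the one already listed as a baseline characteristic and described as a severity measure.
- **Secondary endpoints.** For ADAS-Cog 13 and RBANS, the baseline value in the model is already a cognitive test score, so the argument does not carry over to them.

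A reader might also infer that any chance imbalance in MMSE stays whole in the treatment contrast. It does not. The part shared with baseline CDR-SB, age and the strata is adjusted out, and randomisation is stratified by dementia status.

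These points limit the size and scope of the suggestion. They do not show a cost large enough to reject it.

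**Conclusion.** The point holds as an optional improvement to the CDR-SB model. Baseline MMSE is absent from it, is available before dosing for every eligible patient, and could be added at negligible cost. On the SAP's two-sample assumptions, the gain in power for the first test runs from nothing at a partial R-squared of 0% to about 4.6 percentage points at 10% (67.1% to 71.7%). The documents do not say where in that range, or beyond it, the truth lies.

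A reader might go further and conclude that the plan throws away precision, or that the planned analysis has less than 70% power. The documents support neither. The first needs a prognostic value for MMSE that they do not give. The second reads a simple completer calculation as if it described the repeated-measures model. Nor would MMSE transform the test: 80% power would need a partial R-squared of about 26% on top of the planned covariates. The omission is not an error or an inconsistency.

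**What to change.** Before unblinding, amend SAP 4.4 to add continuous baseline MMSE and an MMSE-by-visit term to the CDR-SB model, so that the Week 73 slope is fitted directly. Define baseline MMSE as the latest pre-dose value, following the SAP's convention for cognitive measures other than CDR-SB and RBANS, and use the same definition in the SAP 4.3 table. Add baseline MMSE to the matching per-visit least-squares sensitivity models for CDR-SB in SAP 4.4.3. A blinded pooled estimate of its partial R-squared, given the planned covariates, could inform the choice. If the sponsor prefers the current model, one sentence of reasoning is enough.

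The cost is a short SAP edit and about one degree of freedom per visit (three visits, about 274 expected completers). No new data are needed. If MMSE adds nothing beyond baseline CDR-SB and dementia status, there is little or no gain and almost no loss.
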